Chronic Kidney Disease (CKD) represents a significant global health issue that imposes a considerable burden on public health systems worldwide [1]. CKD is characterized by a gradual and irreversible decline in kidney function over time [2]. The disease progresses through five stages, eventually leading to End-Stage Renal Disease (ESRD) or kidney failure, where patients typically require dialysis or a kidney transplant to survive [3]. Due to the increasing prevalence of aging populations and potential risk factors such as diabetes and hypertension, the incidence of CKD is rising globally [4]. CKD ranks among the top ten causes of death worldwide [5]. The economic costs associated with CKD are substantial for both individuals and society as a whole [6], particularly for the treatment expenses of ESRD which might be prohibitively expensive in the form of dialysis or kidney transplantation [7]. Many healthcare systems in low- and middle-income countries struggle to cope with these costs [8]. As CKD progresses, affected individuals may experience a variety of complications, including cardiovascular disease, anemia, bone disease, and a decline in quality of life [9], often leading to additional healthcare needs and expenses [10]. This disease can profoundly affect patient's lives, impacting their work and daily activities [11]. Such realities may contribute to increased societal costs, including productivity losses and the need for caregiver support [12]. There are disparities in the incidence and treatment of CKD among different socioeconomic groups and regions, with vulnerable populations often experiencing higher rates of the disease and lacking access to adequate care and treatment options [13]. Efforts to prevent and treat CKD encounter various barriers, such as a lack of symptoms in the early stages leading to late diagnosis, and the complexities of managing the risk factors of the condition [14]. The global burden of CKD is immense, impacting health systems, economies, and the quality of life of patients [1]. There is a need for raised awareness, early intervention, and equitable treatment opportunities to address the challenges posed by this disease.

Non-diabetic Chronic Kidney Disease (CKD) poses a significant clinical challenge, with existing treatment methods having limitations [15]. Available approaches are primarily focused on managing the underlying causes of CKD, such as hypertension and proteinuria, to slow disease progression and prevent complications [16]. Common interventions include lifestyle changes, blood pressure control with Angiotensin-Converting Enzyme inhibitors (ACE inhibitors) or Angiotensin Receptor Blockers (ARBs), and the use of Sodium-Glucose Co-Transporter-2 inhibitors (SGLT2 inhibitors) in certain circumstances [17]. However, for CKD without diabetes mellitus (DM), there remains a vital need for novel treatment options for various reasons [1]. New therapies like finerenone show the potential for such advances. Finerenone is a non-steroidal mineralocorticoid receptor antagonist that has been shown to have benefits in studies on patients with CKD and type 2 diabetes, slowing CKD progression and providing cardiovascular protection [18]. Researchers and clinicians are hopeful that this treatment can also be successfully applied to non-diabetic CKD populations, hence there is interest in further research into its efficacy and safety in this particular group [19].

While current non-diabetic CKD treatment strategies include managing hypertension and proteinuria, there is a clear need for new treatment options [20]. Innovative therapies like finerenone that target specific mechanisms of CKD pathology have the potential to improve outcomes and meet the unmet needs of patients with CKD [21]. Further research and clinical trials

are necessary to explore and validate the efficacy and safety of these new therapeutic approaches [22].

Finerenone holds promise for diabetic CKD; however, the lack of evidence for its use in non-diabetic CKD underlines the importance of further clinical research in this area [23]. Such studies would be incredibly valuable for expanding treatment options and improving outcomes for a broader CKD patient population [24].

Nevertheless, the effectiveness and tolerability of finerenone in patients with non-diabetic chronic kidney disease (CKD) have not yet been clearly established [25]. The design of this study aims to determine whether the renal protective benefits of finerenone also apply to non-diabetic CKD patients, including those with an estimated glomerular filtration rate (eGFR) below 15 ml/min/1.73m² [26]. To our knowledge, our investigation is pioneering in assessing the therapeutic potential and safety profile of finerenone for this specific patient group [27].

II. Research Objective

To assess the progression of kidney disease in non-diabetic CKD patients following the use of finerenone, and to analyze the safety profile of finerenone.

III. Research Content

Investigate the changes in renal function in non-diabetic CKD patients after the administration of finerenone.

Analyze the relationship between the use of finerenone and cardiovascular events.

Evaluate the safety of finerenone treatment.

IV. Research Methodology

(A) Study Design

This project is a single-center, retrospective cohort study.

(B) Study Population

The study population comprises patients who were hospitalized for treatment or followed up on an outpatient basis in the Department of Nephrology, the First Hospital affiliated with Harbin Medical University, starting from December 15, 2023. The baseline for the study is defined as the occasion when a patient with CKD (either as a primary or secondary diagnosis) was first admitted to the nephrology department for hospital treatment or an outpatient visit.

Inclusion criteria:

- (1) Patients who were hospitalized or followed up on an outpatient basis in the Department of Nephrology, the First Hospital affiliated with Harbin Medical University, starting from December 15, 2023;
- (2) Patients with non-diabetic kidney disease;
- (3) Patients with electronic medical records available.

Exclusion criteria:

- (1) Type 2 diabetes mellitus;

(2) Patients who refuse to participate.

(C) Study Variables

In accordance with the research objectives, the project will collect the following variables:

Baseline patient characteristics: including age, gender, stage of kidney disease, comorbidities, medication history, etc.

Use of finerenone: including dosage, duration of therapy, etc.

Kidney-related indicators and cardiovascular events: including eGFR, serum creatinine levels, records of kidney disease events (such as renal function decline, initiation of dialysis, or kidney transplantation), and records of cardiovascular events.

Safety data: including all adverse events recorded.

(D) Data Collection and Data Management

Determine data sources:

The data will primarily be sourced from the hospital's electronic health record HIS system, which may include clinical records, medication administration records, laboratory test results, and radiological reports.

Acquisition of patient information:

Based on the study's inclusion and exclusion criteria, construct a query to compile a list of patients from the hospital database who meet the criteria for CKD.

Creation of data collection forms:

Create a standardized data collection form listing all the information that needs to be gathered.

Ensure the form includes all the key variable items involved in the study.

Data extraction:

Use the search and export functions of the EHR system to export the required data points for each patient involved in the study. This includes the patient's basic information, medication usage, laboratory test results, etc. For information that cannot be collected automatically, such as physicians' notes or qualitative descriptions in radiological reports, manually extract or enter these into the data tables.

Data entry and coding:

Enter the extracted data into the data collection forms. To protect patient privacy, encode patient information wherever possible to anonymize patient identity within the dataset. For qualitative data, such as diagnoses or symptom descriptions, develop a standardized coding system that converts them into quantitative data suitable for statistical analysis.

Quality control:

Perform data cleaning on the preliminary collected data, checking for missing data, outliers, and inconsistencies. Conduct data verification to ensure the accuracy and completeness of all data. If possible, have two research assistants perform data extraction and entry independently and reconcile any discrepancies.

Data storage and security:

Ensure that all electronic data is stored on secure, password-protected servers or cloud services. Regularly back up data to mitigate the risk of data loss.

Ethical compliance:

Ensure that all data collection and processing adhere to the ethical guidelines of the hospital and research institution, local medical regulations, and data privacy laws. If direct communication

with patients is necessary to collect data, obtain informed consent from the patient.

V. Statistical Analysis

In a single-center retrospective study, the data analysis process is complex and multi-step, aimed at extracting meaningful conclusions and insights. Below is a detailed description of the data analysis:

Data cleaning:

Prior to formal analysis, data cleaning is conducted to remove incomplete, incorrect, or inconsistent records.

Missing data are appropriately addressed, for example through imputation or deletion of missing entries.

Duplicate records are checked and resolved to ensure the uniqueness of analysis.

Descriptive statistical analysis:

Descriptive statistical analysis is performed on basic patient characteristics, including age, gender, stage of CKD, etc.

Medication usage of finerenone is quantified (dose, duration of treatment, etc.).

Primary and secondary outcome measures are descriptively analyzed (e.g., changes in renal function, incidence of cardiovascular events).

Exploratory Data Analysis (EDA):

Data within the set is visualized using bar charts, box plots, scatter plots, and other visualization tools to explore potential patterns or trends.

Variables potentially affecting study outcomes are extracted for exploration of relationships between variables.

Hypothesis testing:

If the study aims to compare renal function before and after treatment with finerenone, hypothesis testing might be conducted using parametric or nonparametric methods such as paired sample t-tests or Wilcoxon signed-rank tests.

In the presence of multiple groups (e.g., patients with different stages of CKD), methods such as ANOVA or Kruskal-Wallis may be used to compare differences between groups.

Regression analysis:

Linear regression analysis is conducted to assess the degree of association between continuous variables.

Binary logistic regression analysis is utilized for non-continuous outcome variables, such as the occurrence of cardiovascular events.

Multivariate regression analysis may be applied, if appropriate, to adjust for potential confounding factors.

Survival analysis:

If the study includes analysis of follow-up data, such as tracking the progression of CKD, Kaplan-Meier survival curves can be used for description, and Log-rank tests to assess differences between treatment and control groups.

Cox proportional hazards model could be employed to determine the relationship between

treatment and outcomes while adjusting for confounders.

Use of statistical software:

Complex statistical analyses are performed using statistical software packages such as SPSS, Stata, R, or Python.

Data integrity is maintained throughout the analysis, and all analysis steps are documented for later review.

Interpretation of results:

Attention is given to the levels of statistical significance, and methods like Bonferroni correction are applied to address issues of multiple comparisons.

Statistical findings are translated into clinically meaningful narratives that can be understood and used by physicians or researchers.

Discussion and comparison:

Results are compared with existing literature and other studies to discuss possible reasons for any discrepancies.

Limitations of the study findings are highlighted, and areas needing further research are proposed.

Report writing:

Based on the results of the analysis, a research report or scientific paper is composed, including the methods, data analysis process, results, conclusions, and recommendations.

Through these steps, researchers can effectively draw conclusions from large data sets and provide evidence for clinical decision-making or further research. Throughout all these stages, adherence to statistical principles, data privacy regulations, and ethical guidelines is crucial.

VI. Ethics

Ethical Committee Review

The research protocol, informed consent forms, and any materials directly related to the patients must be submitted to the ethics committee for written approval before the research can formally commence. The ethics committee must be notified in writing upon cessation and/or completion of the study. Researchers are required to promptly report any changes occurring in the research work to the ethics committee (such as revisions to the research protocol and/or informed consent forms) and must not implement these changes prior to obtaining the committee's approval, unless the changes are made to eliminate apparent and direct risks to the enrolled patients.

Informed Consent

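### The only stated baseline is the first nephrology visit, not the start of finerenone, so neither the before/after test nor any treated-versus-control analysis has a time origin that fits the objectives

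*Combined protocol and SAP*

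**What the plan says.** Section IV(B), Study Population, contains the only baseline rule: it is "defined as the occasion when a patient with CKD (either as a primary or secondary diagnosis) was first admitted to the nephrology department", for inpatient treatment or an outpatient visit. The rule does not mention finerenone.

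The aims are anchored on the drug. Section II reads "To assess the progression of kidney disease in non-diabetic CKD patients following the use of finerenone". Section III adds "Investigate the changes in renal function in non-diabetic CKD patients after the administration of finerenone" and "Analyze the relationship between the use of finerenone and cardiovascular events".

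Section IV(C) lists the exposure data as "Use of finerenone: including dosage, duration of therapy, etc"; a start date is not named. Section IV(D) describes the hospital's electronic record as a source "which may include clinical records, medication administration records, laboratory test results, and radiological reports".

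Section V offers three analyses that need a time origin:

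- **Paired tests**, under Hypothesis testing: "If the study aims to compare renal function before and after treatment with finerenone".
- **Logistic regression**, under Regression analysis: "Binary logistic regression analysis is utilized for non-continuous outcome variables, such as the occurrence of cardiovascular events".
- **Kaplan-Meier curves, log-rank tests and a Cox model**, under Survival analysis. These are worded as options. This is the only place where a treatment group and a control group are mentioned.

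No section gives another time origin, an index date for users or controls, a landmark, a time-dependent exposure, or a rule that an outcome must follow the first prescription.

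**The concern.** A patient's first nephrology visit and first finerenone prescription may be the same day or months apart. If they differ, using the visit as time zero does two things.

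- **Before/after test.** This is the analysis that matches the main objective most directly. If the pre-treatment value is the one from the first visit, any change in renal function between that visit and the first prescription is counted as change on finerenone.
- **Treated versus control.** If patients are grouped by whether they ever received finerenone, they are classified by something that happens after time zero. Event-free time and events before the first prescription are then credited to the drug. Covariate adjustment in a Cox or logistic model does not remove this, because the error lies in how time and events are assigned, not in patient mix.

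At stake are the renal result and the cardiovascular association, both stated aims. Either could show a benefit or a harm that does not exist.

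**Working it through.** The documents give no follow-up length, event rate, start delay, share of users or sample size, so there is no figure of theirs to reproduce. Every input below is an assumption.

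**1. Paired test.** Let *s* be the yearly change in eGFR before treatment and *d* the time in years from first visit to first prescription.

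Measured change = (change on finerenone) + *s* × *d*.

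For each 1 ml/min/1.73 m² per year of pre-treatment change, delays of 3, 6 and 12 months add 1 × 0.25 = 0.25, 1 × 0.5 = 0.5 and 1 × 1 = 1.0 ml/min/1.73 m². If function was falling before the start, the error counts against finerenone; if it was recovering, the error favours it. With *d* = 0 it is zero.

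**2. Ever/never comparison, no true effect.** Inputs: constant hazard of 0.1 to 0.3 first events per year; candidates for finerenone *c* = 0.5; starts uniform over *W* = 0.5 years; follow-up *F* = 1.5 years.

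At low event rates the ratio can be found by hand. A candidate spends on average *W*/2 waiting, a fraction *x* = *W*/(2*F*) = 0.5/3 = 0.167 of follow-up.

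*A share b of early events blocks prescribing.* Blocked candidates move, with their event, to the never group:

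ratio ≈ (1 − *bx*) / (1 + *bx* × *c*/(1 − *c*)), with *c*/(1 − *c*) = 1.

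- *b* = 1: 0.833/1.167 = 0.71
- *b* = 0.1: 0.983/1.017 = 0.97
- *b* = 0 (independent prescribing): 1.00

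*An early event prompts a share p of otherwise never-users to start.* They move, with their event, to the ever group. With *c* = 0.5:

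ratio ≈ (1 + *pW*/*F*) / (1 − *pW*/*F*); for *p* = 0.5, *pW*/*F* = 0.167, giving 1.167/0.833 = 1.40.

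Solving the Cox score equation numerically, without the low-rate approximation, gives at 0.1 / 0.2 / 0.3 events per year:

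| Link between early event and prescribing | Ever/never HR |
|---|---|
| Every early event blocks | 0.704 / 0.694 / 0.684 |
| One in ten blocks | 0.966 / 0.965 / 0.963 |
| Independent | 1.000 / 1.000 / 1.000 |
| Prompts half of otherwise never-users | 1.412 / 1.424 / 1.435 |

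The start window matters. If every early event blocks, starts spread over 3 months give 0.82 to 0.84 and over 12 months 0.49 to 0.50. If all users start at the first visit, the ratio is 1.00. Under independent prescribing a true effect is diluted: a true hazard ratio of 0.70 reads about 0.75 with the 6-month window.

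**3. Check of the remedy.** In simulations of 1,000,000 patients per scenario, a Cox model with time before the start counted as unexposed returned 0.99 to 1.02 under no effect, and 0.70 when the true hazard ratio was 0.70.

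**The case against.** The strongest reply is that the error is conditional at each step. The baseline sentence sits under Study Population and may fix only cohort entry and the baseline characteristics. The documents never say that survival time runs from it. They do not say that groups are formed by ever receiving finerenone, and the survival analyses are optional. The logistic model names no treated-versus-control contrast. Collecting duration of therapy normally requires start and stop dates, so the data may already be in hand.

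All of that stands, and it limits the point to a missing rule. It does not remove the point: no other time origin is offered, the aims are anchored on the drug, and nothing excludes the faulty analysis.

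The objection that the figures depend wholly on assumptions also stands. Complete blocking fits death. It is hard to defend for non-fatal cardiovascular events, for which values near 0.96 may be nearer the mark.

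A reader might go further and infer that the plan commits itself to a biased comparison that will favour finerenone. The documents do not support that. They do not describe such a comparison, and the direction depends on how early events relate to prescribing, on which they are silent.

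**Conclusion.** The plan does not specify a time origin suited to its objectives, and the only baseline it states would give wrong results if used as one whenever finerenone starts later than the first visit. The before/after test is affected directly. Treated-versus-control analyses are affected if they are run, and if patients are grouped by ever receiving the drug; the logistic model is affected only if used that way.

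The size cannot be known from the documents. Under the 6-month illustration the null hazard ratio lies anywhere from about 0.69 to about 1.4, including 1.00, so neither sign nor size should be read as a forecast. Nor should a reader infer that start dates are unobtainable: the medication records probably hold them. What is missing is the rule for using them.

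This should be fixed before further analysis, since section VIII reports that 43 cases are organized and preliminary results have already been examined.

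**What to change.** - **Section IV(C):** record finerenone start and stop dates from the same electronic records, including for the 43 cases already organized.
- **Section V, Hypothesis testing:** define the pre-treatment value as the last renal value on or before finerenone start.
- **Section V, Survival and Regression analysis:** make the main treated-versus-control analysis a Cox model with finerenone as a time-dependent covariate, time before the start counted as unexposed. State in advance how time after stopping is classified. Drop ever/never curves and any ever/never logistic model counted from the first visit.
- **Acceptable alternative:** an index-date design, with users followed from the first prescription and controls given a comparable index date at which they are event-free and not yet treated.
- **Patients already on finerenone at the first visit:** analyse separately.

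The cost is wording, date extraction and some extra analysis work. The index-date alternative also loses pre-start person-time. It could be fragile in a small series: 43 patients followed for 18 months at the assumed rates would have about 43 × (1 − e^(−0.15)) = 6 to 43 × (1 − e^(−0.45)) = 16 first events (43 is the number organized so far, not a planned size). These steps correct only the assignment of time and events; adjustment for confounders is still needed.

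### CKD is named but not defined, and the only defined baseline has no stable-function or acute-kidney-injury rule, so recovery from a temporary dip can be counted as change after finerenone

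*Combined protocol and SAP*

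**What the plan says.** The objective (II. Research Objective) is "To assess the progression of kidney disease in non-diabetic CKD patients following the use of finerenone", and the background states that "CKD is characterized by a gradual and irreversible decline in kidney function over time".

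The rules that decide who enters, and when, are these:

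- **Inclusion criterion (2), IV(B):** "Patients with non-diabetic kidney disease". It gives no duration, no eGFR or albuminuria threshold, and does not use the word chronic.
- **Exclusion criteria, IV(B):** type 2 diabetes, and "Patients who refuse to participate". Acute kidney injury is not mentioned.
- **Baseline, IV(B):** the sentence presupposes a CKD label, which may be the main or an additional diagnosis. It fixes the date at the point when that person "was first admitted to the nephrology department for hospital treatment or an outpatient visit". The occasion is not tied to the start of finerenone or to stable kidney function.
- **Case finding, IV(D):** working from the inclusion and exclusion criteria, the team is to "construct a query to compile a list of patients from the hospital database who meet the criteria for CKD". Those criteria for CKD are not stated anywhere.

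Section V allows a paired t-test or a Wilcoxon signed-rank test of renal function before and after finerenone. The wording is conditional, and the plan does not say which measurement is the before value. Section VIII reports that 43 cases have been organised.

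**The concern.** A creatinine taken on admission may reflect an acute-on-chronic injury. If the injury resolves, later eGFR rises whether or not finerenone does anything. With that admission value as the starting point, the rise enters the before/after change with the sign of a renal benefit.

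The same value can put the patient in too severe a CKD stage. That matters because the background says the study covers patients with eGFR below 15, and section V contemplates comparisons by CKD stage. Some patients placed in the lowest group might not have a stable eGFR in that range.

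Nothing else planned removes the problem. Adjustment for confounders in section V is optional and names no covariates. Inpatient or outpatient entry is not named among the variables in IV(C). A larger sample narrows the interval around a biased mean but does not move it.

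**Working it through.** **Text check.** Inclusion (2) read alone asks only for non-diabetic kidney disease. The baseline sentence and the IV(D) query both restrict to CKD, so the plan intends a CKD population. IV(D) refers to criteria for CKD, but the inclusion and exclusion criteria it works from contain none. CKD is thus named and not defined, and criterion (2) does not match the other two places. Allowing CKD as a secondary diagnosis means the reason for admission may be something else. A patient with established CKD and a superimposed acute injury meets every stated rule.

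**Size.** The plan gives no sample size, SD, expected change or power figure, so it has no number of its own to reproduce. What follows is an illustration.

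*Inputs.* n = 43 is the number of cases organised (section VIII), not a planned sample size. All other inputs are assumptions: no drug effect; true mean change μ = -1.5 mL/min/1.73 m² over 6 months; SD of change σ = 6; a share f of patients whose baseline is lowered by a dip d that fully resolves; two-sided 5% paired t-test, critical value 2.018 on 42 df.

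*Formulas.*
- Bias in mean change = f × d
- Observed mean change = μ + f × d
- SD of observed change = √(σ² + d² f(1 − f))
- SE = SD / √43

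*Mildest setting, f = 0.10, d = 5.* Mean = -1.5 + 0.5 = -1.0. SD = √(36 + 25 × 0.09) = 6.18. SE = 0.943. Mean/SE = -1.06. Chance of a significant improvement ≈ P(Z > 2.018 + 1.06) ≈ 0.1%.

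*Most severe setting, f = 0.30, d = 15.* Mean = -1.5 + 4.5 = +3.0. SD = √(36 + 225 × 0.21) = 9.12. SE = 1.391. Mean/SE = 2.16. Chance ≈ P(Z > 2.018 − 2.16) ≈ 56%.

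Simulation with 20,000 runs per setting agrees to within about a percentage point:

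| Share f | Dip d | Bias f × d | Observed mean change | False significant improvement |
|---|---|---|---|---|
| 0 | – | 0 | -1.5 | about 0% |
| 10% | 5 | 0.5 | -1.0 | 0.1% |
| 10% | 10 | 1.0 | -0.5 | 0.6% |
| 10% | 15 | 1.5 | 0.0 | about 2% |
| 20% | 5 | 1.0 | -0.5 | 0.7% |
| 20% | 10 | 2.0 | +0.5 | about 6% |
| 20% | 15 | 3.0 | +1.5 | about 18% |
| 30% | 5 | 1.5 | 0.0 | about 2% |
| 30% | 10 | 3.0 | +1.5 | about 24–25% |
| 30% | 15 | 4.5 | +3.0 | about 55–56% |

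The nominal rate in the improvement direction is 2.5%.

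*Sensitivity to other assumptions.* With σ = 10, the last two rows fall to about 13% and 35%. With μ = 0 and σ = 6, the rate is 7% (f = 10%, d = 5), 42% (20%, 10) and 90% (30%, 15). With n = 150, μ = -1.5, σ = 6, f = 30% and d = 10, it is 68%.

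*Masking a real decline.* With no dips, the test detects the true decline of -1.5 in about 36% of studies. At f = 10% and d = 10, mean = -0.5, SD = √(36 + 100 × 0.09) = 6.71, SE = 1.023, and detection falls to about 7% in simulation.

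**The case against.** The strongest reply is that the plan does restrict to CKD. The baseline sentence requires a CKD diagnosis, and the query selects on CKD. A reader of inclusion (2) alone might infer that anyone with any non-diabetic kidney disease is eligible, including someone with purely acute injury. The full text does not support that. Only the acute-on-chronic case clearly gets through, and it is enough for the point.

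A reader might also infer that recovery *is* counted as drug effect. The documents support only that it *can* be. The paired test is conditional, the before value is unspecified, and baseline may equally be an outpatient visit. The plan does not give the share of inpatient entries, the share with acute injury, or whether finerenone was started during admissions. Nor can the significant differences mentioned in section VIII be put down to this mechanism, because outcome, direction and baseline are not reported there.

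Bias between treated and control patients is a further tempting step. Section V mentions a control group only conditionally and IV(B) defines none, so that remains hypothetical.

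On size, the reply is right that high false-positive rates need large shares and large dips. At a 10% share with μ = -1.5 and σ = 6, the rate stays below the nominal 2.5%. The shift in the mean is present at every setting, and a modest share can still hide a real decline.

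Finally, a rule requiring CKD to be shown over time would not solve this alone. A patient who passes it can still be admitted with a dip. The stable-baseline rule does the work.

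**Conclusion.** The point holds in this form: CKD is undefined, and the one baseline the plan defines lets a temporarily low admission eGFR start the change from baseline. Resolution of such a dip biases the before/after result in finerenone's favour, and staging at that moment can be too severe. This is more than a missing detail, because following the baseline rule as written produces the problem.

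The bias is f × d, from 0.5 to 4.5 mL/min/1.73 m² over the range shown. The rate of false improvement runs from well below nominal to more than half of studies. These figures show direction and range. They are not an estimate for this study, since share, dip, SD and underlying trend are all assumed. Confidence is high on the missing rule and low on how much harm it does here.

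**What to change.** 1. In IV(B), align inclusion criterion (2) with the CKD wording used in the baseline sentence and in IV(D), and state the CKD definition applied.
2. For all eGFR-change analyses, define the starting eGFR as the most recent outpatient or otherwise stable value before the first finerenone dose. Do not use values from an admission with recorded acute kidney injury. The investigators should choose and justify any numeric threshold for creatinine rise or duration, since the documents supply none.
3. Record inpatient or outpatient entry in IV(C), report results by it, and add a sensitivity analysis that excludes inpatient baselines.

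The cost is a change to the query and the data collection form, using creatinine, eGFR and clinical records that IV(C) and IV(D) already plan to collect. The main downside is loss of patients. Baseline is a first nephrology contact in one hospital's records, so those with no earlier stable value leave the main eGFR-change analysis, and they may be a sizeable and selective group. They can stay in the safety description. Report their number and characteristics, and show the all-patient eGFR result alongside the main one.
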